##### Part C:

The Part C SAF includes all patients who were randomized in Part B, entered Part C, and received any study drug in Part C. Efficacy, treatment compliance/administration, and all clinical safety data from Part C through a pre-specified cut-off date around the time of Part B completion will be analyzed for Part C SAF patients who entered Part C from Part B.

The actual treatment group as treated for Part B is defined by the following rules:

- For a patient randomized to dupilumab 300 mg QW or dupilumab 300 mg Q2W, if the patient received all placebo injections in Part B, the actual treatment will be assigned as placebo.
- For a patient randomized to dupilumab 300 mg QW or dupilumab 300 mg Q2W, if the patient received at least one dupilumab injections in Part B, the actual treatment will be assigned as the planned treatment.
- For a patient randomized to placebo, if the patient received at least one dupilumab injections in Part B, the actual treatment will be assigned as dupilumab 300 mg Q2W.

The Part B treatment group assignment for analysis of Part C data will be the same as the SAF for Part B.

For safety summaries, the following analysis periods are defined:

- Part B week 24 treatment period is defined as
  - For patients who entered Part C: Day 1 to the date of first dose of Part C study drug (or week 24 visit if patient entered Part C but never received any Part C study drug).

- For patients who did not enter Part C:
  - Day 1 to the week 24 visit if patients completed week 24 visit with known visit date.
  - Day 1 to study day 169 (24 weeks times 7 days/week), or to patient’s last study participation date, whichever comes earlier, if patients did not complete week 24 visit or had missing week 24 visit date.
- Part C extended treatment period for patients who entered Part C is defined as
  - Time after the first dose of study drug in Part C to the date of week 52 visit if patients completed week 52 with known visit date.
  - Time after the first dose of study drug in Part C to study day 365 (52 weeks times 7 days/week), or to patient’s last study participation date, whichever comes earlier, if patients did not complete week 52 visit or had missing week 52 visit date.
- Follow-up period is defined as
  - For patients who entered Part C: the day after the end of Part C extended treatment period to the patient last study participation date.

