  - For patients who did not enter Part C: the day after the end of Part B week 24 treatment period to the patient last study participation date.

The Part B and Part C SAFs will be the basis for the analyses for the Part B treatment period and Part C treatment period, respectively; however, for the analyses for the follow-up period, only a subset of the corresponding SAFs will be included, which is defined as the patients who entered the follow-up period and had at least one visit after week 24 visit (for Part B SAF) and week 52 visit (for Part C SAF).

Due to COVID-19 pandemic, patients are allowed to extend their current assigned dose regimen of study drug (Part B and/or Part C) until endoscopy with biopsy can be performed at week 24 visit and/or week 52 visit. The safety data during the extended dosing period will also be presented in the corresponding analysis period.

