**Part B (data collected after the first injection in Part C will not be used for Part B analysis)**

**Table 1: Analysis Visit Window for Efficacy Endpoints in Part B**

Visit from SOE	Target Study Day in Part B a	Analysis Visit Window based on Study Day in Part B		
		Histology endpoints, Transcriptome endpoints, EREFS, EndoFLIP endpoints	PGIC, PGIS	EOE-IQ, EoE-SQ, TNSS, RQLQ(S)+12, ACQ-5, POEM
Baseline	1	≤1	≤1	≤1
Week 12	85		[2, 113]	[2, 127]
Week 20	141		[114, 155]	
Week 24 (Part B end of treatment)	169	[2, 190] Error! Reference source not found.	[156, 190] Error! Reference source not found.	[128, 190] Error! Reference source not found.
Week 28 c (Extended period of Part B)	197	[191, 204]		
Week 30 c (Extended period of Part B)	211	[205, 218]		
Week 32 c (Extended period of Part B)	225	[219, 232]		
Week 34 c (Extended period of Part B)	239	[233, 246]		
Week 36 c (Extended period of Part B)	253	≥247		

**Error! Reference source not found.** Study days are calculated from the day of 1st injection of Part B. Study day = (date of assessment – 1st injection date +1) when date of assessment ≥ 1st injection date; otherwise study day = (date of assessment – 1st injection date). If patient never received any dose of study drug, randomization date will be used in place of 1st injection date.

**Error! Reference source not found.** If unscheduled or ET visit occurs in this window and it is after the first dose of Part C, it will be considered for Week 26 in Part C.

c Those are dummy analysis visit windows for patients with extended dosing in Part B. ET or unscheduled visit occurred after week 24 visit and before first dose of part C will be mapped per Table 5.

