**Part C (only applies to patients who received at least 1 dose of Part C study drug)**

**Table 3: Analysis Visit Window for Efficacy Endpoints in Part C**

Visit from SOE	Target Study Day in Part C a	Analysis Window based on Study Day in Part C	
		Histology endpoints, Transcriptome endpoints, EREFS, EndoFLIP endpoints	PRO endpoints
Baseline of Part C	1	≤1	≤1
Week 36	85		[2, 141]
Week 52 (Part C end of treatment)	197	[2, 218]	[142, 218]
Week 56 b (Extended period of Part C)	225		[219, 232]
Week 58 b (Extended period of Part C)	239		[233, 246]

Visit from SOE	Target Study Day in Part C a	Analysis Window based on Study Day in Part C	
		Histology endpoints, Transcriptome endpoints, EREFS, EndoFLIP endpoints	PRO endpoints
Week 60 b (Extended period of Part C)	253	[247, 260]	
Week 62 b (Extended period of Part C)	267	[261, 274]	
Week 64 b (Extended period of Part C)	281	>=275	

**Error! Reference source not found.** Study days are calculated from the day of 1st injection of Part C. Study day = (date of assessment – 1st injection date +1) when date of assessment ≥ 1st injection date; otherwise study day = (date of assessment – 1st injection date). If patient never received any dose of study drug, randomization date will be used in place of 1st injection date.

b Those are dummy analysis visits windows for patients with extended dosing in Part C. ET or unscheduled visit occurred after week 52 visit will be mapped per Table 5.

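### For patients with no completed or dated week-52 visit, the SAP ends the Part C safety period at study day 365, so on-treatment events can fall into follow-up when Part C started late or was extended

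*SAP*

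**What the plan says.** SAP Section 3.2 gives two end rules for the Part C safety period.

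- **Main rule.** The period runs "to the date of week 52 visit if patients completed week 52 with known visit date". No day limit applies.
- **Fallback.** The period is "Time after the first dose of study drug in Part C to study day 365 (52 weeks times 7 days/week"), or to the last participation date, "whichever comes earlier, if patients did not complete week 52 visit or had missing week 52 visit date".

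The Part B period has a similar fallback, "Day 1 to study day 169 (24 weeks times 7 days/week"). It covers only patients who did not enter Part C and have no completed or dated week-24 visit. For patients who entered Part C, the Part B period runs to the first Part C dose or, if none was given, to the week-24 visit.

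Time after the end of a treatment period is follow-up. Follow-up analyses are limited to patients with at least one visit after week 24 (Part B) or week 52 (Part C). On COVID-19 extensions, the same section says: "The safety data during the extended dosing period will also be presented in the corresponding analysis period". It attaches no date rule to that sentence.

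For visit windows, SAP Section 6.4 uses a different origin in each part: "Study days are calculated from the day of 1st injection of Part B" in Table 1 and "Study days are calculated from the day of 1st injection of Part C" in Table 3. Table 3 puts week 52 at Part C day 197.

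**The concern.** The SAP plans for late starts. Blinded Part B dosing may continue until a delayed week-24 biopsy, with no stated maximum (SAP Section 11.2, footnote 6a to the Part B schedule). SAP Section 5.5.2 accepts exposure beyond 24 and 28 weeks. A fallback fixed on the Part B calendar does not follow a Part C period that has shifted or lengthened.

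SAP Section 5.7.1 assigns treatment-emergent events to a period by onset date. An event on Part C treatment after day 365, in a patient under the fallback, therefore leaves the Part C table. It may not reach the follow-up table either, because that table requires a visit after week 52. The Table 5 footnote also makes the follow-up end-of-study visit not applicable to patients who did not complete week 52. Such an event could appear in neither period summary.

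The fallback may also reach patients still being treated. Part C data are analysed to a cut-off around the end of Part B (SAP Sections 3.2 and 8), when some patients will not have reached week 52. Read literally, they have not completed that visit.

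**Working it through.** **Origin of day 365.** Section 3.2 does not define study day, so the origin is inferred.

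- 24 × 7 + 1 = 169 and 52 × 7 + 1 = 365. Both caps follow the same Day 1 convention from the first Part B dose.
- An on-time Part C start on day 169 gives 169 + 28 × 7 = 365.
- The Table 3 target of Part C day 197 maps to 169 + 197 − 1 = 365.
- If day 365 were counted from the first Part C dose, it would fall 365 − 197 = 168 days after the Part C week-52 target. That is not a plausible intent.

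The two anchors therefore agree only when Part C starts on day 169.

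**Late start.** Let S be the study day of the first Part C dose.

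- Planned week 52 = S + 196.
- Days inside the capped period = 365 − S.
- Maximum days past the cap = S + 196 − 365 = S − 169.
- Weekly injections fall on S + 7k, k = 0 to 27. Those later than day 365 are counted.

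The start days are assumptions: day 169 is on time, day 176 is the edge of the +7-day visit window, and days 197, 225 and 253 are extended-period targets in SAP Table 1.

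| S | Planned week 52 | Days kept | Maximum days past cap | Share of 196 | Injections after day 365 (of 28) |
|---|---|---|---|---|---|
| 169 | 365 | 196 | 0 | 0% | 0 |
| 176 | 372 | 189 | 7 | 3.6% | 0 |
| 197 | 393 | 168 | 28 | 14.3% | 3 |
| 225 | 421 | 140 | 56 | 28.6% | 7 |
| 253 | 449 | 112 | 84 | 42.9% | 11 |

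These are maxima. They need a patient under the fallback who is treated and followed to the planned end of Part C. With a dated week-52 visit, or last participation by day 365, the loss is 0 at any S.

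**Extended Part C dosing after an on-time start.** If dosing continues while a week-52 endoscopy is awaited and the visit never takes place, the fallback ends the period at day 365. All on-treatment time after that becomes follow-up.

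**Part B.** The last planned dose is at week 23, day 1 + 23 × 7 = 162, and 162 + 7 = 169. If extended dosing ends with a dose on day L, the on-treatment time past the cap is L + 7 − 169 days, again only for patients under the Part B fallback.

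**The case against.** The strongest reply is that little is left once the conditions are read in full.

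- **Late starters in general.** A reader might infer that everyone whose Part C began late loses events. The documents do not support that, because the main rule follows the actual week-52 date however late it falls.
- **Early leavers.** A reader might infer that the loss falls on patients who leave Part C early with tolerability problems. With a day-253 start, a patient must still be on treatment more than 112 days (16 weeks) into Part C before any treated day passes day 365; with a day-225 start, more than 140 days (20 weeks). Most early leavers fall before the cap, and nothing in the documents shows the affected group to be enriched for tolerability problems.
- **Size.** The start days come from rows of which the SAP says "Those are dummy analysis visit windows for patients with extended dosing in Part B". They do not show that any patient started then.
- **Day 169.** A reader might extend the point to all extended Part B patients. Anyone who entered Part C is outside that cap.
- **Existing safeguard.** Section 3.2 says extended-dosing safety data go to the corresponding period, and SAP Section 4.5.1 keeps events with onset in follow-up as treatment-emergent.

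The first four replies stand and limit the point. The last helps only in part. The sentence on extended dosing gives no date that overrides the fallback, and it does not clearly cover a late starter's ordinary Part C dosing after day 365. Treatment-emergent status is kept, but the summaries are by period.

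**Conclusion.** The fallback rule is wrong as written for a narrow group: patients with no completed or dated week-52 visit, followed on treatment past study day 365, who started Part C late or had extended Part C dosing. On a literal reading this can include patients still in Part C at the data cut-off. Their later on-treatment events are classed as follow-up and may miss that summary too, contrary to the SAP's own statement on extended dosing and its Part C day-197 target.

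The most that can be misassigned is 28, 56 or 84 of 196 days for the three assumed delayed starts. The conclusion rests on the inferred Part B origin of the day count. The number of affected patients is unknown and could be zero. The point concerns descriptive safety summaries, not efficacy testing, so it is minor. The Part B counterpart is narrower still: extended Part B dosing, no entry to Part C, and no completed or dated week-24 visit.

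**What to change.** In SAP Section 3.2:

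- Set the Part C fallback end to the later of first Part C dose + 196 days and last Part C dose + 7 days, still limited by last study participation or the data cut-off. The 7 days match the exposure formula in SAP Section 5.5.2.
- Set the Part B fallback end to the later of day 169 and last Part B dose + 7 days, limited by last participation.
- Define the study-day origin, and state that patients still in Part C at the cut-off are handled by this rule.

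The cost is a wording change and one date derivation. For an on-time patient without extended dosing, 169 + 196 = 365. The last planned Part C dose is on day 169 + 27 × 7 = 358, and 358 + 7 = 365, so nothing changes. For Part C starts on day 197, 225 or 253 the first term moves to day 393, 421 or 449.

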### **3.3. The Pharmacokinetic Analysis Set (PKAS)**

The PK analysis set for Part B and Part C includes all randomized patients who received any study drug and who had at least one non-missing drug concentration result following the first dose of study drug in the corresponding study part.

### **3.4. The Immunogenicity Analysis Set**

The ADA analysis set (AAS) for Part B and Part C includes all patients who received any study drug and had at least one non-missing ADA result from the dupilumab ADA assay after first dose of the study drug in the corresponding study part. Patients will be analyzed according to the treatment actually received.

The neutralizing antibody (NAb) analysis set (NAS) for Part B and Part C includes all treated patients who received any study drug (active or placebo), have at least one non-missing ADA

result following the first dose of study drug (active or placebo), and either tested negative at all ADA sampling times or tested positive for ADA with at least one non-missing NAb result after first dose of the study drug (active or placebo) in the corresponding study part. Patients who are ADA negative are set to negative in the NAb analysis set. Patients will be analyzed according to the treatment actually received.

### 3.5. Subgroups

Subgroups are defined by key baseline factors recorded on the eCRF (unless otherwise specified) and listed as follows.

Subgroups to be considered for both efficacy and safety analyses:

- Age group (years; 12 to <18, ≥18)
- Sex (Male, Female)
- Duration of EoE (years from start date of EoE to randomization date; <5, ≥5)
- Baseline weight group (<60 kg, ≥60 kg)
- Prior use of swallowed topical steroids (STC) for the treatment of EoE (Yes, No)
- Inadequate response, intolerant and/or contraindicated to swallowed topical corticosteroids (STC) (Yes or No)
- History of atopic dermatitis (Yes, No)
- History of asthma (Yes, No)
- History of allergic rhinitis (Yes, No)
- History of food allergy (Yes, No)

Note: subgroups defined by race, ethnicity, and region are not included as majority of patients in Part B are anticipated to be in one major category of these demographic factors. The analysis for the subgroups defined above may not be performed if the number of patients within the subgroup is small, e.g. <20 patients per arm.

Subgroups to be considered for efficacy analyses only:

- Baseline BMI group (<25, ≥25-<30, ≥30)
- Use of PPI at randomization (Yes, No)
- Prior esophageal dilations (Yes, No)
- Subject on a food elimination diet at the time of screening (Yes, No)
- Subject on a food elimination diet in the past (Yes, No)

## 4. ANALYSIS VARIABLES

### 4.1. Demographic and Baseline Characteristics

The following demographic and Baseline characteristics variables will be summarized:

- Demographic variables: Age at screening as a continuous variable and with grouping (years; 12 to <18, ≥18 to <40, ≥40 to <65, ≥65), Sex (Male, Female), Ethnicity with grouping (Hispanic or Latino, Not-Hispanic or Latino), Race with grouping (White, Black or African American, Asian, Other), Region (North America, or Rest of World), Country, Baseline weight as a continuous variable and with grouping (kg; <60, ≥60), Height (m), and calculated BMI (kg/m^2; <15, ≥15-<25, ≥25-<30, ≥30), age [years; 12 to <18, ≥18] and use of PPI at randomization [Yes, No].
- Baseline characteristics:
  - DSQ total score
  - Number of days with dysphagia in the 2 weeks prior to baseline as a continuous variable and with group (4, 5, 6, 7, 8, etc.)
  - Amount of pain patient had experienced when swallowing food from DSQ
  - Peak esophageal intraepithelial eosinophil count (eos/hpf) of three regions (proximal, mid, and distal)
  - Eosinophilic Esophagitis-Endoscopic Reference Score (EREFS) total score
  - Mean stage score from the EoE Histology Scoring System (EoEHSS) summed over 3 regions
  - Mean grade score from the EoEHSS summed over 3 regions
  - Total EoEHSS histology stage score (excluding lamina propria fibrosis) summed over 3 regions
  - Total EoEHSS histology grade score (excluding lamina propria fibrosis) summed over 3 regions
  - Patient global impression of severity (PGIS) level (none, mild, moderate, or severe)
  - EoE Impact Questionnaire (EoE-IQ) score
  - EoE Symptom Questionnaire (EoE-SQ) frequency score and severity score
  - Total Nasal Symptom Score (TNSS) for patients with history of allergic rhinitis
  - Rhinoconjunctivitis Quality of Life Questionnaire score for patients aged 12+ years [RQLQ(S)+12] for patients with history of allergic rhinitis
  - Asthma Control Questionnaire-5 (ACQ-5) score for patients with history of asthma
  - Patient-Oriented Eczema Measure (POEM) score for patients with history of atopic dermatitis
  - European quality of life 5-dimensional scale (EQ-5D) utility index score

- European quality visual analogue scale (EQ VAS)
- Baseline blood eosinophil count as a continuous variable and with grouping (Giga/L; <0.15, ≥0.15; <0.30, ≥0.30; <0.50, ≥0.50)
- Baseline serum total immunoglobulin E (IgE) as a continuous variable and with grouping (IU/mL; <100, ≥100)
- Patients treated with PPI at randomization (Yes, No)
- Prior use of STC for EoE (Yes, No)
- Effectiveness of prior use of swallowed topical corticosteroids for EoE (Yes, No)
- Inadequate response, intolerant and/or contraindicated to STC (Yes or No)
- Prior esophageal dilations (Yes, No)
- Prior use of STC for EoE and prior esophageal dilation (Yes, No)
- Number of prior esophageal dilations
- Age at the first esophageal dilation with grouping (years; 0 to 11, 12 to 18, 19 to 24, 25 to 50, >50), calculated as the number of years between patient birth year and the year of the first esophageal dilation (prior to screening)
- Duration of EoE as a continuous variable and with grouping (years; <5, ≥5)
- Age at EoE onset with grouping (years; 0 to 11, 12 to 18, 19 to 24, 25 to 50, >50), calculated as the number of years between patient birth year and the start year of EoE
- Historical esophageal biopsy showing ≥ 15 (eso/hpf [400 X]) after 8 weeks of high-dose PPI (Yes, No)
- Patient on food elimination diet in past (Yes, No)
- Patient on food elimination diet at screening (Yes, No)

#### European Quality of Life 5-Dimensional Scale (EQ-5D)

The European Quality of Life 5-dimension (EQ-5D) scale is a standardized questionnaire used to assess health status ([Rabin R, Gudex C, Selai C, Herdman M. From translation to version management: a history and review of methods for the cultural adaptation of the EuroQol five-dimensional questionnaire, Value Health 2014 Jan;17\(1\):70-76.](#)) ([Brooks R. EuroQol: the current state of play, Health Policy. 1996 Jul;37\(1\):53-72.](#)). It consists of a descriptive system and the EQ visual analogue scale (EQ VAS). The EQ-5D-3L (3-level) descriptive system comprises of the following 5 dimensions: mobility, self-care, usual activities, pain/discomfort, and anxiety/depression. For each dimension, patients select one of 3 levels: no problems, some problems, and extreme problems. Health states defined by the 5-dimension classification can be converted into corresponding index scores that quantify health status. This utility index score is ranged from -0.594 to 1 (perfect health). The algorithm and SAS code for the utility index scoring are provided in Appendix 11.8. The EQ VAS records the patient's self-rated health on a vertical visual analogue scale where the endpoints are labelled 'Best imaginable health state'

(100) and ‘Worst imaginable health state’ (0). The EQ-5D-3L will be completed at screening or baseline visit by patients screened under protocol amendment 3 or later.

## 4.2. Medical History

Medical history will be coded using MedDRA. Same MedDRA version will be used for Part B data and Part B patients’s data in Part C within the scope of DBL. Information related to EoE and other atopic medical conditions includes diagnosis of EoE, atopic dermatitis, asthma, allergic rhinitis, allergic conjunctivitis, chronic rhinosinusitis, nasal polyps, food allergy, hives, contact dermatitis, and other allergies [medications, animals, plants, mold, dust, mites, etc.]. Patient dietary status at the time of screening is also collected with information on whether patient is on food elimination diet, food type eliminated, and reason for elimination of specific food.

## 4.3. Pre-treatment / Concomitant Medications and Procedures

Medications/Procedures will be recorded from the day of informed consent until the EOS visit.

Medications will be coded using WHO Drug Dictionary (WHODD). Patients will be counted once in each medication class linked to the medication. Medications of interest include PPIs and swallowed topical/systemic corticosteroids for the treatment of EoE.

Procedures will be coded per MedDRA.

Pre-treatment medications/procedures: medications taken or procedures performed prior to administration of the first dose of study drug.

Concomitant medications/procedures (CMs/CPs): medications taken or procedures performed following the first dose of study drug through the EOS visit. This includes medications that were started before the study and are ongoing during the study. Furthermore, CM/CP will be categorized according to analysis periods (as defined in Section 3.2):

- CMs/CPs taken during the Part B week 24 treatment period
- CMs/CPs taken during the Part C extended active treatment period
- CMs/CPs taken during the follow-up period

Prohibited concomitant medications/procedures during the study:

Treatment with the following concomitant medications is prohibited through week 52:

- Swallowed topical corticosteroids (may be used as rescue treatment for EoE)
- Systemic corticosteroids (may be used as rescue treatment for EoE)
- Systemic immunosuppressive/immunomodulating drugs (including, but not limited to, omalizumab, cyclosporine, mycophenolate-mofetil, azathioprine, methotrexate, IFN- $\gamma$ , or other biologics)
- Treatment with an investigational drug (other than dupilumab)
- Initiation, discontinuation, or change in dosage regimen of the following medications within 8 weeks prior to the baseline endoscopy (stable doses of these medications are allowed)

- Proton pump inhibitors, unless used for a required PPI trial during the screening period or in patients who present at the initial screening visit with current use of PPIs
- Systemic leukotriene inhibitors
- Nasal and/or inhaled corticosteroids
- Initiation of SCIT, or change in dose for those patients on a stable dose of SCIT within 1 year prior to screening
- SLIT
- OIT
- Treatment with an investigational drug (other than dupilumab)
- Treatment with a live (attenuated) vaccine (see protocol Section 7.1.1 for the list of vaccine).

The following concomitant procedures are prohibited during study treatment (through week 52):

- Major elective surgical procedures
- Esophageal dilation (may be used as rescue procedure)
- Initiation or change of food-elimination diet regimen

Patients may receive the prohibited medications/procedures listed above as needed during the follow-up period, with the exception of live (attenuated) vaccine, which should not be used within 3 months after the last dose of study drug. Investigators are advised to prescribe prohibited medications/procedures judiciously, only when they are absolutely required for the appropriate management of study patients.

Blinded adjudication of prohibited medications and procedures will be performed by the medical monitor before database locks with documented procedures.

Rescue treatments (including both medications and procedures): If medically necessary (eg, for treatment of intolerable EoE symptoms), rescue medications (systemic and/or swallowed topical corticosteroids) or emergency esophageal dilation are allowed for study patients in Part B and C. If possible, an endoscopy with biopsy will be performed prior to the initiation of rescue therapy. Patients who undergo an endoscopy with biopsy due to the initiation of rescue therapy will not undergo the scheduled end of treatment visit endoscopy/biopsy at weeks 24 and 52. Patients who receive rescue treatment in Part B will not be eligible for the Part C extended active treatment period unless an endoscopy with biopsy is performed prior to the initiation of rescue treatment. However, if the endoscopy with biopsies cannot occur due to COVID-19 restrictions, rescue treatment should not be delayed, and these patients will be eligible for Part C. Patients receiving rescue therapy may continue to receive study drug. They will remain blinded and will be asked to return to the clinic for all remaining study visits and participate in all assessments for these visits except for endoscopy/biopsy, as noted above.

Blinded adjudication of rescue treatments will be implemented before database locks by considering the type of medication or procedure, indication, timing, frequency and the potential

impact of the use of the medication or procedure. The rescue treatments will be adjudicated by the medical director (or medical monitor) with documented procedures.

